2.4.4.2 Analyses of secondary efficacy endpoints

For continuous secondary efficacy parameters (see [Section 2.1.3](#)) with missing data at baseline, missing data will be imputed using MI under the missing at random (MAR) assumption. Missing data at baseline will be imputed using regression method that includes randomization strata of Week -1 HbA1c ($\leq 8.5\%$, $> 8.5\%$), randomization strata of Week -1 SBP (< 130 mmHg, ≥ 130 mmHg), randomization strata of sulfonylureas use at Week -1 (yes, no), and baseline value in the imputation model.

Each continuous secondary efficacy endpoint ([Section 2.1.3](#)) will be analyzed using a similar ANCOVA model including the measurements at baseline and endpoint (observed or imputed). The missing data at endpoint will be imputed by the retrieved dropouts if there are at least 5 patients in each study treatment group who discontinued but have the endpoint data. Otherwise,

the washout imputation method will be used. After the imputation, each of the complete datasets will be analyzed by an ANCOVA model.

The ANCOVA model will include treatment groups (sotagliflozin 400 mg, 200 mg, and placebo), randomization stratum of HbA1c ($\leq 8.5\%$, $> 8.5\%$), randomization stratum of SBP (< 130 mmHg, ≥ 130 mmHg), randomization strata of sulfonylureas use at Week -1 (yes, no), and country as fixed effects, and the corresponding baseline of secondary endpoint value as a covariate. For the analysis of SBP in patients with baseline SBP ≥ 130 mmHg, the randomization stratum of SBP will not be included. Results from each complete dataset will be combined using Rubin's formula to provide the adjusted mean change from Baseline to Week 18 (or Week 12 for SBP, week 52 for HbA1c and BW) for each treatment group, as well as the between-group differences and the 95% CIs for the differences.

For all continuous secondary endpoints, summary statistics at scheduled visits will be provided for each treatment group. The summary will include the number of observations, mean, SD, SE, minimum, median, and maximum. Graphical presentations will also be used to examine trends over time using mean values (\pm SE) and mean changes from baseline (\pm SE) at each of the scheduled visits. In addition, SBP will be summarized descriptively at each visit for those patients with baseline SBP ≥ 140 mmHg.

The categorical secondary and other efficacy variables of HbA1c $< 6.5\%$, $< 7\%$ at Week 18 will be analyzed respectively using a Cochran-Mantel-Haenszel (CMH) method stratified by randomization stratum of HbA1c ($\leq 8.5\%$, $> 8.5\%$), randomization stratum of SBP (< 130 mmHg, ≥ 130 mmHg), and randomization strata of sulfonylureas use at Week -1 (yes, no). The proportion in each treatment group will be provided, as well as the difference of proportions between sotagliflozin (400 mg, 200 mg) and placebo with associated 2-sided 95% CI. For HbA1c responders at Week 18 ($< 6.5\%$, $< 7\%$ respectively), all values at Week 18 will be used to determine whether a patient is a responder or not, even if they are measured after IMP discontinuation or rescue medication use. Patients who have no HbA1c measurement at Week 18 will be treated as non-responders. Summary tables and graphs will also be provided by treatment group at scheduled visits.

For between-group comparison, a sensitivity analysis will be performed respectively for HbA1c $< 6.5\%$ responder analysis by excluding patients whose HbA1c values at baseline are $< 6.5\%$, and for HbA1c $< 7\%$ responder analysis by excluding patients whose HbA1c values at baseline are $< 7\%$ using the same CMH test mentioned above. Similarly, by-visit summary may also be provided excluding those patients.

2.4.4.3 Analyses of other efficacy endpoints

Except for PRO endpoints, the analysis of other endpoints (see [Section 2.1.3](#)) will be descriptive with no formal testing. Summary statistics at scheduled visits will be provided by each treatment group. Graphical presentations will also be used to illustrate trends over time. For the daily Lantus dose (U) and daily Lantus dose adjusted by body weight (Lantus dose/body weight in U/Kg),

summary statistics (for screening value, run-in value, baseline value, and observed values) at scheduled visits (using OC) will also be provided for each treatment group.

The change from baseline values will be summarized for UGE and UGCR. These 2 variables have been added for analyses.

For the daily Lantus dose and total daily insulin dose, the baseline value is defined as the available value on the last day prior to the first dose of double-blind IMP for those randomized and exposed or before randomization for those who were randomized but never exposed to IMP.

The number (%) of patients achieving HbA1c response (<6.5%, <7% at Week 18, Week 26 and Week 52, respectively) will be descriptive summarized at each scheduled visit.

The number (%) of patients who used rescue therapy and a KM curve for the time to first rescue therapy will be provided by treatment group during the entire 52-week treatment period (see [Section 2.5.4](#)). A list of patients who used rescue therapy will also be provided.

UACR will be log-transformed at patient level. Summary statistics of UACR in log scale will then be calculated for each treatment group at each visit and back-transformed to provide the geometric mean and its associated percent change of UACR from baseline.

Shift tables will be provided for UACR at Week 26 and Week 52 using the pre-defined categories. That is, the number (%) of patients with progression from one category at baseline to another category at Week 26 and Week 52 will be provided by treatment group. The pre-defined categories are, for UACR, <30 mg/g creatinine [Normal], ≥30 to <300 mg/g creatinine [Microalbuminuria], and ≥300 mg/g creatinine [Macroalbuminuria].

The analysis of TRIM-D scores is in [Section 2.4.7](#).

2.4.4.4 Multiplicity issues

To control for the family wise type I error, a fixed-sequence procedure will be applied to the primary and key secondary endpoints to the following order:

Once the main study primary variable (change from Baseline to Week 18 in HbA1c comparing sotagliflozin 400 mg versus placebo) is statistically significant at $\alpha = 0.05$ (2-sided), the following secondary efficacy variables will be tested in the following prioritized order. The testing will stop as soon as an endpoint is found to be not statistically significant at $\alpha = 0.05$ (2-sided).

- Comparing sotagliflozin 400 mg versus placebo:
 - Change from Baseline to Week 18 in FPG
 - Change from Baseline to Week 18 in BW.
 - Change from Baseline to Week 12 in SBP for patients with Baseline SBP ≥ 130 mmHg
 - Change from Baseline to Week 12 in SBP for all patients

-
- Change from Baseline to Week 52 in HbA1c
 - Change from Baseline to Week 52 in BW
 - Comparing sotagliflozin 200 mg versus placebo:
 - Change from Baseline to Week 18 in HbA1c
 - Change from Baseline to Week 18 in BW
 - Change from Baseline to Week 18 in FPG.
 - Change from Baseline to Week 12 in SBP for patients with Baseline SBP \geq 130 mmHg
 - Change from Baseline to Week 52 in HbA1c
 - Change from Baseline to Week 52 in BW

If any hypothesis is found to be not statistically significant, the testing procedure will be stopped and the following hypotheses will not be tested.

No multiplicity adjustment will be made on other secondary efficacy variables than mentioned above.

2.4.4.5 Analyses of CGM sub-study efficacy variables

The analysis of CGM endpoints will be performed on the CGM sub-study population using CGM measurements obtained during the study, including those obtained after IMP discontinuation or introduction of rescue therapy.

All CGM derived variables will be subject to the following criteria.

- CGM data are masked to both the patients and investigators.
- A complete 24-hour CGM profile includes 288 data points given that CGM reading is recorded every 5 minutes.
- The start and end time of a 24-hour CGM profile is defined as midnight, i.e. each CGM profile begins at midnight (0.00) and ends at midnight (23:59). Partial CGM data points prior to the first midnight and after the last midnight from the visit will not be used in the CGM parameter calculation as the partial CGM profile may introduce additional variabilities to the data.
- Useable CGM data for a day/a 24-hour CGM profile are defined as at least 80% time of records (230 data points) without a gap (missing data) lasting for \geq 2 hours per 24 hours.
- Qualified CGM data for calculating baseline value should have at least 4 days (not necessarily consecutive) of useable 24-hour CGM data from 7-day CGM profiles. Qualified CGM data for calculating the post randomization value at Week 19 should have at least 4 days (not necessarily consecutive) of useable 24-hour CGM data from 14-day CGM profiles.

- In case that there are more than 288 data points or more than one data point per 5 minutes, usually due to recalibration or switching CGM devices, averaging the data points every 5 minutes will be performed so that there is only one data point per 5 minutes.
- For all CGM parameters except the standard deviation of glucose levels between days, AUC of glucose concentrations for 2 hours after a standardized mixed meal and 2-hour PPG, a CGM parameter will be first calculated based on each 24-hour CGM profile from the visit, the final values of the CGM parameters for the visit will be based on the average of parameter values taken on each CGM profile from each CGM visit.
- The percentage of time glucose within or outside a specific range will be calculated as time of CGM glucose within/outside the range divided by total time with valid data.

Analysis of CGM sub-study primary endpoint

The CGM primary endpoint of change in percentage of time glucose levels within the target range of 70 to 180 mg/dL (3.9 to 10.0 mmol/L) over 24 hours from baseline to Week 19 will be analyzed by an ANCOVA model using the values measured at baseline and Week 19 (observed or imputed). The missing CGM values at endpoint will be imputed by multiple imputation (MI) methods as described below.

Note that the comparison of change in percentage of time glucose levels within the target range of 70 to 180 mg/dL (3.9 to 10.0 mmol/L) over 24 hours from baseline to Week 19 between sotagliflozin 200 mg and placebo is a CGM sub-study secondary endpoint, however the analysis is identical to that of CGM primary endpoint and is detailed here for concision.

Missing endpoint data at Week 19 visit will be imputed using a model built separately in each treatment group and estimated from the patients in the same treatment group who prematurely discontinue the IMP before the Week 19 visit but have the measurement for the endpoint (retrieved dropouts). The imputation model will include the randomization strata and the corresponding baseline value. In cases of non-convergence during the imputations, the offending stratum will be identified and then will be dropped from the model. Considering that the number of patients in each treatment group who discontinue the IMP but have the measurement for the endpoint is expected to be small, a simple imputation model based on regression will be used with baseline measurement included as the predictor. This will serve as the primary model of imputation for missing data should sampling criteria be satisfied (see below).

An alternative (back-up) imputation method will be used if the number of patients who prematurely discontinue the IMP before the Week 19 visit but have the measurement for the endpoint is <5 in any treatment groups (ie, not sufficient retrieved dropouts to support the imputation method described above). This criterion will be assessed for each CGM sub-study primary or continuous secondary endpoint.

In the back-up imputation method, missing post-baseline endpoint values at Week 19 will be imputed by washout multiple imputation (MI) method under the missing not at random (MNAR) framework.

Missing endpoint data at Week 19 in the sotagliflozin group(s), as well as in the placebo group are imputed from a model estimated from patients in the placebo group who have the endpoint data available.

For patients in the sotagliflozin 400 mg and 200 mg groups with missing data at Week 19, their missing values will be imputed using observed baseline and the observed primary endpoint data from placebo completers; no intermittent values from either placebo or the active treatment groups will be used.

For placebo patients, missing data will be imputed based on the placebo group data. Intermittent observed values will be used while imputing missing values at Week 19. In cases that a non-monotone missing data pattern occurs at the intermediate visits, these data points will be first imputed in the placebo group using the Markov Chain Monte Carlo (MCMC) option in PROC MI to achieve a monotone missing pattern for all placebo patients. The Week 19 endpoint values will be subsequently imputed from the multiple copies of the original dataset where each copy will have a monotone missing pattern.

The imputation models for the washout MI method will include the randomization strata and the corresponding baseline value. Missing data will be imputed using the regression method. In cases of non-convergence during the imputations, especially for the MCMC application in the placebo non-monotone datasets, graphical measures (eg, trace and autocorrelation plots) will be used to identify the offending variable and once detected, that variable(s) will be dropped from the model and the imputations will be re-run. These re-run models will use the same seed number and number of imputations as used in the original models.

Using either imputation method, missing endpoint data will be imputed multiple times to generate multiple data sets with complete data. Each of the complete datasets after the imputation will be analyzed by the ANCOVA model with treatment arms (sotagliflozin 400 mg, sotagliflozin 200 mg, and placebo), randomization strata of Week -1 HbA1c ($\leq 8.5\%$, $> 8.5\%$), randomization strata of Week -1 systolic blood pressure (< 130 mmHg, ≥ 130 mmHg), randomization strata of sulfonylureas use at Week -1 (yes, no), Lantus injection time (morning, evening) and country, as fixed effects, and Baseline CGM percentage value as a covariate. Results from each complete dataset will be combined to provide the adjusted mean change of percentage of time inside the target range (≥ 70 to ≤ 180 mg/dL) from Baseline to Week 19 for each treatment group, as well as the between group difference (comparing the sotagliflozin 400 mg, 200 mg versus placebo), and the 95% confidence interval (CI).

For the purpose of categorizing Lantus injection time (morning, evening), the available Lantus injection time on the last day prior to the first dose of double-blind IMP for those randomized and exposed or before randomization for those who were randomized but never exposed to IMP will be used. The injection time during the period of 0:00 to 11:59 will be in morning category and in evening category if the injection time is during the period of 12:00 to 23:59. If the patient is using Lantus more than once daily, the category will be based on the injection time of the largest dose. If the doses are equal, the injection time of the latest dose will be used.

Summary statistics at scheduled visits will be provided for each treatment group. The summary will include the number of observations, mean, SD, SE, minimum, median, and maximum. Graphical presentations will also be used to examine trends over time using mean values (\pm SE) and mean changes from baseline (\pm SE) at each of the scheduled visits.

Analyses of CGM sub-study secondary endpoints

Continuous CGM secondary endpoints will be analyzed using a similar approach as the CGM sub-study primary endpoint, with missing post-randomization CGM values (ie, final values of the CGM parameter) imputed by the retrieved dropouts imputation method or by the washout imputation method according to the criterion described in [Section 2.4.4.5](#).

For each of the continuous CGM sub-study secondary endpoints, each of the complete datasets will be analyzed by the ANCOVA model with treatment groups (sotagliflozin 400 mg, sotagliflozin 200 mg, placebo), randomization strata of Week -1 HbA1c ($\leq 8.5\%$, $>8.5\%$), randomization strata of Week -1 SBP (<130 mmHg, ≥ 130 mmHg), randomization strata of sulfonylureas use at Week -1 (yes, no), Lantus injection time (morning, evening) and country as fixed effects, and Baseline secondary endpoint value as a covariate. Results from each complete dataset will be combined to provide the adjusted mean change from Baseline to Week 19 (Week 18 for MMTT related endpoints) for each treatment group, as well as the between group difference (comparing each sotagliflozin group versus placebo), and the 95% CI using contrast statement.

For all continuous CGM sub-study secondary endpoints, summary statistics at scheduled visits will be provided for each treatment group. The summary will include the number of observations, mean, SD, SE, minimum, median, and maximum. Graphical presentations will also be used to examine trends over time using mean values (\pm SE) and mean changes from Baseline (\pm SE) at each of the scheduled visits (using OC).

Mean 24-hour glucose concentration is calculated by sum of glucose values divided by total number of glucose measurements for the 24 hourly intervals and then averaged for the period before each visit.

The CV over 24-hour is calculated as the ratio of the standard deviation of the glucose values to mean of the glucose values over 24-hour profile. For each patient and visit, the CV from all CGM profiles will be averaged as the final values of the CV for the visit. It will be log-transformed before the analysis. Change from Baseline to Week 19 of CV in log scale will be analyzed. Results in the log scale will be back-transformed.

AUC of glucose concentrations for 2 hours after a standardized mixed meal will be calculated using the linear trapezoidal method. CGM data will be limited to CGM readings taken from the start of the standardized meal through 2 hours after the start of the standardized meal, inclusive.

The analysis of the 2-hour PPG endpoint following a standardized mixed meal will be based on a Time 0 adjusted value (ie, the 2-hour PPG value minus the Time 0 value, FPG sample) at both the

Baseline and Week 18 time points. These Time 0 adjusted values will be used to derive the Week 18 minus Baseline scores, which will serve as the measure of interest for comparative purposes.

Analyses of CGM sub-study other endpoints

The analysis of other sub-study endpoints (see [Section 2.1.3](#)) will be descriptive with no formal testing. Summary statistics at scheduled visits using observed cases will be provided by each treatment group.

The details for calculation AUCs outside of target ranges, MAGE and SD of glucose levels within and between days (24-hour CGM profile) are provided below.

Inter-quartile range (IQR) is determined by calculating the difference between the 75th and 25th percentile values for the 24 hourly intervals over each 24-hour CGM profile and then averaged for the period of each visit.

A hypoglycemic episode is defined as a set of any number of consecutive CGM glucoses, all of which are <70 mg/dL (< 3.9 mmol/L) for at least 15 minutes. No provisions are made for gaps in measurements.

Calculation of CGM sub-study parameters

1) Mean Amplitude of Glycemic Excursion (MAGE)

It is defined as mean glucose value by summing absolute rises and falls (local minima and maxima) of more than 1 SD (within a 24-hour CGM profile). It includes only peak-to-nadir or nadir-to-peak excursions. $MAGE_j = \sum \frac{\lambda}{n}$ if $\lambda > SD$, where λ is the glucose increase or decrease (peak-to-nadir or nadir-to-peak excursions for the jth 24-hour CGM profile). n is the number of peak-to-nadir or nadir-to-peak excursions for the jth 24-hour CGM profile.

2) Standard deviation of glucose levels (SD) of glucose levels within and between days and coefficient of variation

$SD_{within,j} = \frac{\sum (x_{ij} - \bar{x}_j)^2}{h_j - 1}$, where x_{ij} is individual CGM data points within the jth 24-hour CGM profile, \bar{x}_j is the mean glucose reading from all CGM data points for the jth 24-hour CGM profile. h_j is number of CGM data points within the jth 24-hour CGM profile. For each patient and visit, the $SD_{within,j}$ from all CGM profiles will be averaged as the final values of the within SD for the visit.

$SD_{between} = \frac{\sum (\bar{x}_j - \bar{x})^2}{m - 1}$ where \bar{x} is the mean glucose reading from all evaluable CGM data points from all evaluable CGM profiles from the same visit for the patient. \bar{x}_j is the mean glucose reading from all CGM data points within the j^{th} 24-hour CGM profile. m is the number of evaluable 24-hour CGM profiles,

$$CV = \frac{\sum \frac{SD_{within,j}}{\bar{x}_j}}{m}$$

where \bar{x}_j is the mean glucose reading from all CGM data points within the j^{th} CGM 24-hour profile.

3) *Calculations of glucose AUC outside target ranges (daily average over the period prior to a visit)*

Calculations of glucose AUC of hyperglycemia (hypoglycemia) are described as follows.

Let t_i represent the time of each CGM glucose measurement and Δx_i equals the absolute value of change from target at each time point.

The glucose AUC outside target range at each time point will be determined using the following formulas:

- $AUC_i = (t_i - t_{i-1})(\Delta x_i + \Delta x_{i-1})/2$ if the both measurements are above (below) the target range
- $AUC_i = (t_i - t_{i-1})(\Delta x_i^2 / (\Delta x_i + \Delta x_{i-1}))/2$ if the first measurement is below (above) the target range and the second measurement is above (below) the target range
- $AUC_i = (t_i - t_{i-1})(\Delta x_{i-1}^2 / (\Delta x_i + \Delta x_{i-1}))/2$ if the first measurement is above (below) the target range and the second measurement is below (above) the target range
- $AUC_i = 0$ if both measurements are below (above) the target range

The CGM glucose AUC for the full 24 hours will be calculated as the sum of the AUC_i values using the available CGM data within the 24-hour CGM profile. The daily average will be calculated from this sum.

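### The MAGE denominator is defined over all excursions, not only those above 1 SD; the two SD formulas also need checking for a missing square root

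*SAP*

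**What the plan says.** All the relevant text is in SAP section 2.4.4.5, mostly under the calculation of CGM sub-study parameters.

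**MAGE.** The prose reads: "It is defined as mean glucose value by summing absolute rises and falls (local minima and maxima) of more than 1 SD", with the SD taken within a 24-hour profile. The formula sums λ/n over excursions, subject to λ > SD, where λ is the size of a single rise or fall. The denominator is then described in a plain sentence: "n is the number of peak-to-nadir or nadir-to-peak excursions for the jth 24-hour CGM profile". The 1 SD condition is not repeated there.

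**SDs.** As extracted, the within-day formula begins "SD_{within,j} = \frac{\sum (x_{ij} - \bar{x}_j)^2}{h_j - 1" and the between-day formula begins "SD_{between} = \frac{\sum (\bar{x}_j - \bar{x})^2}{m - 1". Neither shows a square root. The SAP adds that "the $SD_{within,j}$ from all CGM profiles will be averaged as the final values of the within SD for the visit".

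**CV.** The text on secondary sub-study endpoints says: "The CV over 24-hour is calculated as the ratio of the standard deviation of the glucose values to mean of the glucose values". The later formula averages the within-day SD divided by the daily mean over the evaluable profiles.

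**Status.** Change in CV to Week 19 is a secondary sub-study endpoint (SAP section 2.1.3.4). It is analyzed by ANCOVA on the log scale, with a between-group difference and 95% CI. MAGE and the two SDs are other sub-study endpoints, summarized descriptively without formal testing.

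**The concern.** The prose and the definition of n describe two different quantities. If the sum takes only large excursions and the denominator counts all of them, every small turn in the trace lowers MAGE. A complete profile has 288 readings, and the SAP gives no smoothing rule, so small turns could be numerous.

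The shortfall is not a fixed factor. It depends on how many small excursions a patient has at a given visit, so it need not cancel in the change from baseline. A change in the number of small turns would move the literal MAGE even if the large excursions stayed the same.

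The missing root is a separate matter. If it is truly absent from the plan, the quantities labeled SD are variances in squared units. The CV formula would then no longer match the CV that the SAP defines in words.

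**Working it through.** The documents give no numerical MAGE, SD or CV, so there is no stated figure to reproduce. The glucose values below are assumptions chosen for illustration.

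**1. MAGE, general form.** Let N be the number of excursions in a profile, k the number with λ > SD, and S the sum of those k values.
- Intended (prose): S / k
- Literal (n as defined): S / N
- Hence literal = intended × k / N

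The two agree only when every excursion exceeds 1 SD (k = N). Otherwise the literal value is too small.

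**2. MAGE, simple example.** Assume N = 12, k = 4, and a mean of 90 mg/dL for the four large excursions.
- S = 4 × 90 = 360
- Intended: 360 / 4 = 90 mg/dL
- Literal: 360 / 12 = 30 mg/dL
- Factor: 4 / 12 = 0.33

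**3. MAGE, constructed profile.** An assumed smooth 288-point day with three main peaks and a few minor ones has SD 30.2 mg/dL and N = 13 excursions. Six exceed 1 SD: 115.0, 69.2, 47.6, 40.4, 68.2 and 61.9 mg/dL.
- S = 402.3
- Intended: 402.3 / 6 = 67.1 mg/dL
- Literal: 402.3 / 13 = 30.9 mg/dL
- Factor: 6 / 13 = 0.46

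**4. SD formulas, conditional on the root being absent in the source.** The printed expressions, a sum of squares over a count minus 1, would then be variances. For the constructed day the result is 910 (mg/dL)² instead of 30.2 mg/dL.

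The position of the root matters, because the within-day quantity is averaged over profiles. For two assumed days with SD 30 and 60:
- Mean of the SDs: (30 + 60) / 2 = 45
- Root of the mean variance: √((900 + 3600) / 2) = √2250 = 47.4

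The SAP averages the daily SDs, so the root belongs inside each profile.

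**5. CV, under the same condition.** With assumed SD 50 and mean 170 mg/dL, the verbal definition gives 50 / 170 = 0.294. The rootless formula gives 2500 / 170 = 14.7, which carries units of mg/dL and so is not a coefficient of variation. The log transformation would not remove the discrepancy. For an assumed change to SD 40 and mean 155:
- Ratio by the verbal definition: (40 / 155) / (50 / 170) = 0.877
- Ratio by the rootless formula: (1600 / 155) / (2500 / 170) = 0.702

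**The case against.** **On MAGE.** The intent is clear from the prose. The condition λ > SD follows the whole term λ/n, and λ and n are described in nearly the same words, so a programmer may well read n as the count of the λ values being averaged. This stands as far as it goes: miscalculation is not certain. But the sentence defining n carries no restriction and, read literally, contradicts the prose. It is an ordinary sentence, so loss of a mathematical symbol does not explain it.

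**On the SDs.** A square root lost in PDF extraction would disappear from both formulas alike, which is what is seen. Fractions, bars and subscripts survived, but that does not exclude the loss of the radical. The heading, the symbols and the averaging sentence all name a standard deviation, and the verbal CV definition does too. This objection largely stands, and the point can only be put as a check.

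**On the source.** The Protocol (section 6.1) refers CGM procedures, endpoints and analyses to a separate substudy protocol, which was not available here. The formulas may be correct there. That would not remove the need for the SAP to be right.

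**Conclusion.** The MAGE point holds at low severity. As defined, n makes the formula disagree with its own prose, and literal coding shrinks MAGE by the factor k / N. In the assumed examples that factor is 0.33 and 0.46; its actual size depends on patients' traces and could be as mild as 1.

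The SD point is only a query to be settled against the source document. A reader might infer that both SDs are variances, that CV is therefore computed wrongly, and that the MAGE threshold is a variance which few or no excursions could pass. The documents do not support asserting this. The root may have been lost in extraction, CV is defined in words as standard deviation over mean, and the MAGE text sets its threshold at 1 SD by name. The 30 versus 90 example itself uses a true SD as the threshold, so it cannot be combined with a variance threshold.

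MAGE and both SDs are descriptive. CV is a secondary sub-study endpoint outside the fixed testing sequence of SAP section 2.4.4.4, and it would be affected only if the root is truly missing and the formula is followed over the verbal definition. Nothing here touches a main-study result or the primary sub-study endpoint.

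**What to change.** 1. In SAP section 2.4.4.5, define n as the number of excursions with λ > SD in the jth 24-hour profile.
2. Check the source document for the square root in the within-day and between-day SD formulas. If it is absent, add it to both, taking the within-day root for each profile before averaging over profiles.
3. Confirm that the CV formula uses that per-profile SD, so that it matches the verbal definition in the same section.
4. Check any MAGE, SD and CV programs already written against the clarified formulas.

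The cost is a small text and formula correction in the SAP. Data collection, sample size and study conduct are unaffected.
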